## 4.2 Exclusion Criteria

Patient exclusion criteria include any of the following:

1. Prior exposure to CDK 4/6 inhibitor therapy
2. History of retinal disease or active visual disturbances (normal baseline study-specified retinal exam required).
3. Acute illness, including infections requiring medical therapy, known bleeding diathesis or need for anticoagulation.
4. Treatment with any of the following medications within 4 weeks before the baseline diagnostic biopsy is taken:
  - a. Oral estrogens, including hormone replacement therapy (but prior depot estrogen use not allowed).
  - b. Investigational agents (or 5 half-lives, whichever is longer).
5. Required concomitant use of any drug that is a strong CYP3A inhibitor or inducer.
6. Psychological, familial, sociological or geographical conditions that do not permit compliance with the study protocol.
7. Life expectancy of less than 6 months.
8. Pregnancy, lactation or planning to be pregnant.
9. Neo-adjuvant cohorts (Phase II): Prior therapy for breast cancer (medical, surgical or radiation therapy)
10. Neo-adjuvant cohorts (Phase II): Clinical T4 disease.

11. Neo-adjuvant cohorts (Phase II): Inoperable or metastatic (Stage IV) breast cancer based on standard evaluation.

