#### **5.2.6 Review of Systems and Physical Exam**

A full review of systems that covers all of the domains and systems represented in CTCAE V 4.03 toxicity criteria will be performed at screening/baseline. Subsequent physical exams may be limited and should be focused on sites of disease to explore clinical signs and symptoms.

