#### **6.2.3 Dosing of hydroxychloroquine and dose adjustments for hydroxychloroquine**

HCQ will be given by mouth at the assigned dose for the Phase I dose escalation and Phase II fixed dose parts of the trial. The dose of 400 mg daily was chosen as the starting dose for the Phase I portion as this is the usual dose used clinically and has been combined with endocrine and other and cancer therapies at this dose in prior studies.P34-37P There will be no dose adjustments for HCQ, and any grade 3 toxicity that is attributed to HCQ will require discontinuation of drug and for the patient to come off study. Subsequent treatment will be as per standard of care. For patients on the Phase I portion, any Grade III toxicity attributed to HCQ will also be counted as a dose-limiting toxicity if occurring in the first 28 days.

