## APPENDIX B - Hydroxychloroquine (Plaquenil) Package Insert

### PLAQUENIL®

### HYDROXYCHLOROQUINE SULFATE, USP

#### WARNING

PHYSICIANS SHOULD COMPLETELY FAMILIARIZE THEMSELVES WITH THE COMPLETE CONTENTS OF THIS LEAFLET BEFORE PRESCRIBING HYDROXYCHLOROQUINE.

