## 29. CONTRAINDICATIONS

Use of this drug is contraindicated (1) in the presence of retinal or visual field changes attributable to any 4-aminoquinoline compound, (2) in patients with known hypersensitivity to 4- aminoquinoline compounds, and (3) for long-term therapy in children.

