## 30. WARNINGS, General

PLAQUENIL is not effective against chloroquine-resistant strains of *P. falciparum*.

Children are especially sensitive to the 4-aminoquinoline compounds. A number of fatalities have been reported following the accidental ingestion of chloroquine, sometimes in relatively small doses (0.75 g or 1 g in one 3-year-old child). Patients should be strongly warned to keep these drugs out of the reach of children.

Use of PLAQUENIL in patients with psoriasis may precipitate a severe attack of psoriasis. When used in patients with porphyria the condition may be exacerbated. The preparation should not be used in these conditions unless in the judgment of the physician the benefit to the patient outweighs the possible hazard.

**Usage in Pregnancy**—Usage of this drug during pregnancy should be avoided except in the suppression or treatment of malaria when in the judgment of the physician the benefit outweighs the possible hazard. It should be noted that radioactively-tagged chloroquine administered intravenously to pregnant, pigmented CBA mice passed rapidly across the placenta. It accumulated selectively in the melanin structures of the fetal eyes and was retained in the ocular tissues for five months after the drug had been eliminated from the rest of the body.

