## 32. OVERDOSAGE

The 4-aminoquinoline compounds are very rapidly and completely absorbed after ingestion, and in accidental overdosage, or rarely with lower doses in hypersensitive patients, toxic symptoms may occur within 30 minutes. These consist of headache, drowsiness, visual disturbances, cardiovascular collapse, and convulsions, followed by sudden and early respiratory and cardiac arrest. The electrocardiogram may reveal atrial standstill, nodal rhythm, prolonged intraventricular conduction time, and progressive bradycardia leading to ventricular fibrillation and/or arrest. Treatment is symptomatic and must be prompt with immediate evacuation of the stomach by emesis (at home, before transportation to the hospital) or gastric lavage until the stomach is completely emptied. If finely powdered, activated charcoal is introduced by the stomach tube, after lavage, and within 30 minutes after ingestion of the tablets, it may inhibit further intestinal absorption of the drug. To be effective, the dose of activated charcoal should be at least five times the estimated dose of hydroxychloroquine ingested. Convulsions, if present, should be controlled before attempting gastric lavage. If due to cerebral stimulation, cautious administration of an ultrashort-acting barbiturate may be tried but, if due to anoxia, it should be corrected by oxygen administration, artificial respiration or, in shock with hypotension, by vasopressor therapy. Because of the importance of supporting respiration,

tracheal intubation or tracheostomy, followed by gastric lavage, may also be necessary. Exchange transfusions have been used to reduce the level of 4-aminoquinoline drug in the blood.

A patient who survives the acute phase and is asymptomatic should be closely observed for at least six hours. Fluids may be forced, and sufficient ammonium chloride (8 g daily in divided doses for adults) may be administered for a few days to acidify the urine to help promote urinary excretion in cases of both overdosage and sensitivity.

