Retinopathy may progress even after the drug is discontinued. In a number of patients, early retinopathy (macular pigmentation sometimes with central field defects) diminished or regressed completely after therapy was discontinued. Paracentral scotoma to red targets (sometimes called "premaculopathy") is indicative of early retinal dysfunction which is usually reversible with cessation of therapy.

A small number of cases of retinal changes have been reported as occurring in patients who received only hydroxychloroquine. These usually consisted of alteration in retinal pigmentation which was detected on periodic ophthalmologic examination; visual field defects were also present in some instances. A case of delayed retinopathy has been reported with loss of vision starting one year after administration of hydroxychloroquine had been discontinued.

**Dermatologic Reactions:** Bleaching of hair, alopecia, pruritus, skin and mucosal pigmentation, photosensitivity, and skin eruptions (urticarial, morbilliform, lichenoid, maculopapular, purpuric, erythema annulare centrifugum, Stevens-Johnson syndrome, acute generalized exanthematous pustulosis, and exfoliative dermatitis).

**Hematologic Reactions:** Various blood dyscrasias such as aplastic anemia, agranulocytosis, leukopenia, anemia, thrombocytopenia (hemolysis in individuals with glucose- 6-phosphate dehydrogenase (G-6-PD) deficiency).

**Gastrointestinal Reactions:** Anorexia, nausea, vomiting, diarrhea, and abdominal cramps. Isolated cases of abnormal liver function and fulminant hepatic failure.

**Allergic reactions:** Urticaria, angioedema and bronchospasm have been reported.

**Miscellaneous Reactions:** Weight loss, lassitude, exacerbation or precipitation of porphyria and nonlight-sensitive psoriasis.

Cardiomyopathy has been rarely reported with high daily dosages of hydroxychloroquine.

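### Section 4.2 does not exclude known hypersensitivity to 4-aminoquinolines, a contraindication in the appended hydroxychloroquine insert, and no other eligibility item covers it

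*Combined protocol and SAP*

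**What the plan says.** **Eligibility (Sections 4.1 and 4.2).** Each section has 11 numbered items. The HCQ-specific item is exclusion 2: "History of retinal disease or active visual disturbances (normal baseline study-specified retinal exam required". Section 1.4 explains it as a measure against retinal toxicity based on American Academy of Ophthalmology guidance.

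**HCQ insert (Appendix B, Contraindications).** Three contraindications are listed: retinal or visual field change caused by a 4-aminoquinoline; use "in patients with known hypersensitivity to 4- aminoquinoline compounds"; and long-term treatment of children.

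**HCQ insert (Appendix B, Warnings, General).** HCQ may provoke a severe attack of psoriasis and may worsen porphyria. The insert says that it "should not be used in these conditions unless in the judgment of the physician the benefit to the patient outweighs the possible hazard".

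**HCQ dosing (Sections 3.2.2, 3.5 and 6.2.3).** The Phase I dose levels are 400, 600 and 800 mg daily. Phase II uses 400 mg in Part 1 and the recommended Phase II dose in Part 2. HCQ doses are not adjusted, and "any grade 3 toxicity that is attributed to HCQ will require discontinuation of drug and for the patient to come off study".

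**Baseline work-up (Sections 5.2.1 and 5.2.6).** Screening includes "A full review of systems that covers all of the domains and systems represented in CTCAE V 4.03 toxicity criteria". The baseline list does not name a drug-allergy history.

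**The concern.** The eligibility list decides who may be given the study drug, and Section 9.5 requires an eligibility checklist for every enrolled patient. A contraindication that is not on the list does not make anyone ineligible, even if it is recorded in the chart.

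The gap matters more for HCQ than for the other two drugs. Palbociclib and letrozole are standard treatment for the Phase I patients, and letrozole is the standard endocrine drug in Phase II. Being a candidate for standard therapy therefore says something about whether a patient can take letrozole, but nothing about whether she can take HCQ.

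At stake is a preventable exposure. The insert lists allergic reactions among its adverse effects: "Urticaria, angioedema and bronchospasm have been reported". Weekly visits and the grade 3 stopping rule can only respond to a reaction once it has happened, whereas an exclusion works before the first dose. Phase II patients also have operable, potentially curable disease, and Section 1.4 concedes that four weeks of treatment may not change their outcome.

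**Working it through.** The plan states no figure on this point, and no formula applies. The check sets the insert's list against the numbered criteria.

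**Inputs.** Section 4.1 has 11 items and Section 4.2 has 11, so 11 + 11 = 22 numbered items. Appendix B gives three contraindications and one conditional warning that names two conditions.

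| Appendix B | Status in the insert | Matching item in 4.1 or 4.2 |
|---|---|---|
| 4-aminoquinoline retinal or field change | Contraindication | Exclusion 2 (broader than the insert) |
| Long-term use in children | Contraindication | Inclusion 4 (age 18 or over) |
| Known 4-aminoquinoline hypersensitivity | Contraindication | None of 22 |
| Psoriasis | Conditional warning | None of 22 |
| Porphyria | Conditional warning | None of 22 |

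Contraindications reflected: 2 of 3. Contraindications missing: 3 − 2 = 1. Conditions under the conditional warning that are addressed: 0 of 2.

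**Could a general item cover the missing contraindication?** The candidates are:

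- Exclusion 3 concerns acute illness, bleeding tendency and anticoagulation, not drug allergy.
- Exclusion 6 concerns circumstances that prevent compliance.
- Inclusion 7 (Phase I) requires suitability for a CDK4/6 inhibitor with an aromatase inhibitor. HCQ is neither.
- Inclusion 11 (Phase II) requires suitability for surgery and for pre-operative endocrine therapy. HCQ is not endocrine therapy.
- No item excludes a patient because the investigator considers her unsuitable in general.

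**Is it handled elsewhere in Sections 1 to 9?** Hypersensitivity to HCQ, psoriasis and porphyria are not mentioned there. Section 6.2.1 refers the reader to Appendix B in general terms. Section 6.4 restricts only strong CYP3A inhibitors and inducers. The Section 6.2.3 rule is triggered by a toxicity that has already occurred.

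**Result.** A patient with a known 4-aminoquinoline allergy who is otherwise eligible satisfies all 22 items.

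**The case against.** The best case for the plan is that the eligibility list is not the only barrier before dosing. The insert is part of the protocol, states the contraindication outright, and opens with the instruction "PHYSICIANS SHOULD COMPLETELY FAMILIARIZE THEMSELVES WITH THE COMPLETE CONTENTS OF THIS LEAFLET BEFORE PRESCRIBING HYDROXYCHLOROQUINE". Screening includes a full review of systems. A careful physician who knew of the allergy would not prescribe HCQ. On psoriasis and porphyria, the insert itself leaves the decision to the physician, and a silent protocol leaves that discretion intact.

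Much of this stands. The documents do not show that such a patient would be dosed; they show only that the stated criteria would not stop it. But making information available does not make a patient ineligible. The protocol did not leave retinal disease or pregnancy to clinical judgment; it wrote both in as exclusions. Psoriasis and porphyria remain a secondary point because the warning is conditional.

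A reader might infer more than the documents support:

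- **That the retinal exclusion was taken selectively from the insert.** Section 1.4 attributes it to ophthalmology guidance, and exclusion 2 is wider than the insert's wording.
- **That the Overdosage text proves rapid allergic harm.** It says "or rarely with lower doses in hypersensitive patients, toxic symptoms may occur within 30 minutes", but the symptoms it goes on to list are those of acute toxicity, such as drowsiness, cardiovascular collapse and convulsions. It does not say that the hypersensitivity was known beforehand. The allergic reactions listed under Adverse Reactions are likewise not tied to patients with a known history.
- **That all 54 planned patients (18 + 6 + 30) will receive HCQ.** In Phase II it starts only after the day 15 biopsy, and Section 5.2.3.2 takes patients off study if Ki67 at that biopsy exceeds 10%. Section 8.0 makes Part 1 conditional on a recommended dose of 600 or 800 mg. Phase I could stop after 2 patients (Section 3.8).
- **That letrozole hypersensitivity is a parallel gap.** Section 1.4 describes Phase I patients as candidates for standard palbociclib and letrozole. For Phase II, inclusion 11 together with Section 6.3 reasonably covers it.

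**Conclusion.** The point holds for HCQ hypersensitivity. One of three labelled contraindications to the experimental drug is absent from all 22 eligibility items, and no other clause covers it. The criteria as written admit such a patient to HCQ at 400 to 800 mg daily, with protection only after exposure.

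This is an inexpensive safety improvement, not a flaw that undermines the trial. The documents give no prevalence of 4-aminoquinoline hypersensitivity, psoriasis or porphyria, so the number of patients affected cannot be stated and may be zero. No effect on the dose-limiting toxicity rate, the endpoint, power or sample size is claimed. The conclusion rests on reading Section 4 as the complete eligibility rule; nothing in Sections 1 to 9 suggests otherwise.

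**What to change.** 1. Add one exclusion to Section 4.2, applying to both phases: known hypersensitivity to hydroxychloroquine or any other 4-aminoquinoline.
2. Add a matching history question to the baseline assessments in Section 5.2.1, and carry the new item onto the eligibility checklist.
3. As a secondary change, list psoriasis and porphyria as exclusions unless the investigator documents that expected benefit outweighs the hazard. This keeps the discretion that the insert allows and leaves a record that it was used.

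The cost is two lines of protocol text and a short addition to the baseline history. A few otherwise eligible patients may be excluded; the documents do not allow an estimate of how many. Visits, endpoints, decision rules and sample size stay as they are.

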### 1.3 Rationale for the Use of Pre-operative (Neoadjuvant) or “Window” Endocrine Therapy

We have chosen to perform this trial using the combination of letrozole, palbociclib and HCQ in the pre-operative (neoadjuvant) “window” setting after careful deliberation internally and advice

from both internal and external advisory board members during the process of a grant proposal submission that led to the successful funding of both the laboratory and clinical trial aims of this project. However, the initial lead-in Phase I safety trial that includes HCQ dose escalation with the study regimen of continuous low dose palbociclib and letrozole and the determination of the recommended Phase 2 dose (RP2D) for HCQ will be conducted in patients with advanced metastatic breast cancer, followed by activation of the neoadjuvant/window trial.

The following rationale support this approach:

- Palbociclib is already FDA-approved for metastatic breast cancer with an excellent safety record. It is currently in several clinical trials in both the neoadjuvant and adjuvant settings.
- Treatment will include letrozole, a standard endocrine therapy as is used clinically for early stage breast cancer.
- HCQ is an approved drug commonly used for malaria and autoimmune disease and particularly safe when used at the doses and timeframes proposed (see more expanded description in Section 6.2).
- This model allows for safe biopsies as needed for the correlative tissue aims and eliminates artifact and variability due to prior therapies as all patients will be previously untreated.
- The design gives patients and their physicians the option of a brief “window” trial with 4 weeks on study drug (2 weeks on low dose palbociclib plus letrozole, then 2 weeks with the addition of HCQ) then to proceed with surgery or a research biopsy if additional standard of care neoadjuvant therapy is indicated, and then followed by standard of care.
- The very first exposure to the combination will be performed in a cohort of patients with advanced breast cancer using a standard “3+3” Phase I HCQ dose escalation scheme in combination with the study regimen of low dose continuous palbociclib with letrozole. Once safety is established at the specific HCQ dose level, the corresponding arm of the Phase II neoadjuvant/window trial will be activated. This approach will maximize safety by only moving to early stage curable population once safety of the study regimen is established in the advanced setting.

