### 3.3 Dose Limiting Toxicity (DLT) Definition

A DLT will be defined as:

- Any death not clearly due to the underlying disease or extraneous causes
- Any grade 3 or higher non-hematologic toxicity
- Liver function abnormalities meeting Hy's law
- Neutropenic fever
- Grade 4 neutropenia or thrombocytopenia > 7 days
- Grade 3 or higher thrombocytopenia with bleeding

- Grade 3 or higher nausea/vomiting or diarrhea  $\geq$  72 hours with adequate antiemetic and other supportive care
- Grade 3 or higher fatigue  $\geq$  1 week
- Grade 3 or higher electrolyte abnormality that lasts  $>72$  hours, unless the patient has clinical symptoms, in which case all grade 3 or higher electrolyte abnormality regardless of duration should count as a DLT.

All AEs of the specified grades should count as DLTs except those that are clearly and incontrovertibly due to disease progression or extraneous causes.

The decision to open the Phase II window part of the trial will be made after RP2D has been established. All Safety Data will be reviewed by the Principal investigator and will be used to determine whether the study proceeds to the “window” Phase II trial in the neo-adjuvant setting.

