C= Phase I – baseline biopsy can of metastatic tumor pre-treatment or primary lesion (optional) or can be from archival tissue if available (either primary or metastasis). Week 5 biopsy (optional) can be +/- 1 week. Phase II – biopsies are mandatory- third biopsy done either at W5 for patients going on to surgery at that time, for those waiting until between weeks 20-24, biopsy done pre-operatively. Patients who know in advance that they will proceed with surgery at T2 will not need a biopsy and biomarkers will be measured on the surgical specimen. Imaging will be done at end of Cycle 2 (Week 8) +/- 1 week (prior to cycle 3 drug), and every 8-12 weeks (+/- 2 weeks) thereafter

D= Phase II – Sample of surgical specimen (or core needle biopsy if patients is going on to standard of care neoadjuvant endocrine or chemotherapy) will be taken for analysis as outlined in Section 5.3.

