## **5.3 Correlative Biomarker Studies**

### **5.3.1 Biopsies, Tissue Handling and Analysis**

All biopsies on Phase I are optional and will be done with appropriate image guidance.

Biopsies for Phase II are mandatory and will be done under ultrasound guidance by a member of the research team using standard of care imaging-guided biopsy. Local anesthesia and hemostasis protocols will be used as per standard protocol. Core needles of 18 or 16G size will be used and 3-4 core biopsies will be obtained. The first core will be placed in standard 10% formalin, and all other cores will be placed in a cryovial and snap frozen in liquid nitrogen.

All of the correlative studies (unless otherwise indicated) will be performed in the laboratory of [name] located in the Zayed building at [name]. For all the correlative analysis we will use tumor tissues collected from the biopsies and at surgical resections.

Cyclin E, and Rb immunohistochemistry (IHC) assays. FFPE tumor tissue slides will be prepared from paraffin imbedded blocks per standard methodologies and subjected to IHC analysis with 2 different antibodies: cyclin E and Rb:

Cyclin E: the anti-human C-19 polyclonal antibody (Santa Cruz Biologicals) at 1:2000 dilution will be used to stain each slide. Each slide will be scored for percent nuclear and percent cytoplasmic positive staining. Only tumor cells with greater than 5% nuclear or cytoplasmic positivity are considered as cyclin E positive. Nuclear and cytoplasmic staining scores are assigned according to the staining intensity (0 = no staining, 1 = blush staining, 2 = weak staining, 3 = intermediate staining and 4= strong staining). The nuclear and cytoplasmic scores are then combined, and four immunophenotypes are identified. First, breast tumors will be considered to be negative for cyclin E when staining is not detected in the nuclei or cytoplasm (phenotype 1). Second, in cases determined to be cyclin E+, if the nuclear staining score exceeded the cytoplasmic score, cyclin E expression is defined as predominantly nuclear (phenotype 2). Third, when the nuclear and cytoplasmic staining scores are equal,

cyclin E expression is considered to be both nuclear and cytoplasmic (phenotype 3). Fourth, if the cytoplasmic staining score is higher than the nuclear score, cyclin E expression is considered to be predominantly cytoplasmic (phenotype 4).

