## 6.4 Concomitant Medications

In general, the use of any concomitant medication or therapies deemed necessary for the care of the patient is permitted with the exception of strong CYP3A inhibitors or inducers.

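### The washout in exclusion 4 is counted back from a baseline biopsy that Phase I patients may not have or that may be archival, so the weeks before cycle 1 day 1 are left unrestricted

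*Combined protocol and SAP*

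**What the plan says.** Section 4.2, item 4, excludes "Treatment with any of the following medications within 4 weeks before the baseline diagnostic biopsy is taken". Two classes follow. Item 4a is "Oral estrogens, including hormone replacement therapy (but prior depot estrogen use not allowed", and item 4b is "Investigational agents (or 5 half-lives, whichever is longer". Items 9 to 11 of the same list are marked as Phase II only. Item 4 is not, so it governs both phases.

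The biopsy rules differ by phase:

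- **Phase I.** Section 5.3.1 states: "All biopsies on Phase I are optional and will be done with appropriate image guidance". Footnote C to the tables in section 5.2 says the baseline sample may be an optional pre-treatment biopsy, "or can be from archival tissue if available (either primary or metastasis". No age limit is given. Section 5.2.1 restricts the fresh baseline biopsy to Phase II.
- **Phase II.** Biopsies are mandatory (5.3.1). Figure 2 in section 3.2.2 labels T0 as the baseline, pretreatment sample. Table 2 with footnote A puts the baseline biopsy within 2 weeks before therapy starts.

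On concomitant treatment, section 6.4 says that, in general, "any concomitant medication or therapies deemed necessary for the care of the patient is permitted with the exception of strong CYP3A inhibitors or inducers". It names neither class listed in item 4.

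**The concern.** A washout criterion needs a reference date that exists for every patient it governs and that lies close to the period it bears on. In Phase I the baseline diagnostic biopsy meets neither condition. With no study biopsy, there is no date to count from. With archival tissue, or with the original diagnostic specimen as a fallback, the date may be months or years old, and item 4 then says nothing about what the patient took last month.

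This bears on the Phase I primary endpoint. DLTs are assessed over the first 28-day cycle (section 3.2, Phase I design). Under section 3.3, "All AEs of the specified grades should count as DLTs except those that are clearly and incontrovertibly due to disease progression or extraneous causes". A toxicity that emerges or worsens in that cycle, and that might come from a recent investigational agent, is hard to call incontrovertibly extraneous, so it would tend to count. Cohorts hold 3 to 6 patients. Two DLTs close a dose level, and two at the starting level end the regimen as not feasible. The resulting RP2D is the hydroxychloroquine dose for the 30 patients of Phase II Part 2 (section 3.5).

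**Working it through.** The plan gives no figure to reproduce here. The check is a cross-reading of the rules plus date arithmetic.

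**1. Which days the rule covers.** Let B be the days from the reference biopsy to first dose, and W the washout length: 28 days, or 5 half-lives for an investigational agent if that is longer. Item 4 covers day −(B + W) to day −B. The last B days before first dose are uncovered, whatever W is.

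| Situation | B | Window covered (W = 28) | Days before first dose left uncovered |
|---|---|---|---|
| Phase I, no study biopsy | undefined | none | criterion cannot be evaluated |
| Phase I, archival tissue | no upper limit | day −(B + 28) to −B | B, unlimited |
| Phase I, example with B = 365 (assumed) | 365 | day −393 to −365 | 365 |
| Phase II, reference = T0 | 0 to 14 | at the earliest, day −42 to −14 | at most 14 |

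**2. Whether the original diagnosis rescues Phase I.** Section 5.2.1 expects a pathological diagnosis for every patient, so some diagnostic specimen should exist. It carries no time limit for Phase I, so B is still unbounded.

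**3. Whether another rule closes the gap.** Item 4 is the only time-limited drug washout in sections 4.1 and 4.2. Item 9, on prior breast cancer therapy, is limited to Phase II. The bar on earlier CDK4/6 inhibitors does not reach other investigational agents. Section 6.4 excepts only strong CYP3A inhibitors and inducers. The one partial exception is depot estrogen, which item 4a disallows regardless of timing.

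**4. Whether a treatment anchor would be foreign to this protocol.** It would not. Inclusion 4e counts 28 days from oophorectomy to first study treatment, and footnote A in section 5.2 places Phase I laboratory tests within 14 days of cycle 1 day 1.

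**5. What could reach the DLT count.** Section 7.1 treats a condition present before study drug as an adverse event only if it worsens afterwards. Stable residual toxicity therefore drops out, and new or worsening carry-over toxicity remains. The documents do not say how many patients would have had a recent investigational agent, or how often such toxicity would follow, so no rate can be derived.

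**The case against.** The other side has real points.

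- **Purpose.** The protocol never states what the washout is for. A biopsy anchor makes sense for protecting baseline Ki67 in Phase II. A reader might infer that the rule fails a treatment period it was written to protect, but the text does not say that was its aim. What stands is narrower: in Phase I the stated reference date does not work.
- **Phase II.** A reader might infer that a woman on oral hormone replacement at diagnosis could never enter, or that the listed agents distort the Ki67 > 5% entry test. The first needs the reference to be the clinical diagnostic core instead of T0. If the reference is T0, item 4 clears the listed agents for 4 weeks before that sample. The word diagnostic leaves some doubt, because section 5.2.1 lists the pathological diagnosis and the fresh biopsy separately. That calls for a clarification.
- **Safeguards on DLTs.** Besides section 7.1 and the exception in 3.3, entry requires adequate blood counts and renal and liver function, ECOG 0–1 and no acute illness. These narrow the route to harm without removing delayed or worsening toxicity.
- **Size.** It is tempting to put a number on the harm. At an assumed 10% DLT risk, a level clears for escalation with probability 0.9³ + 3(0.1)(0.9²)(0.9³) = 0.729 + 0.177 = 0.906. With one spurious DLT certain among the first three patients, it is 0.9⁵ = 0.590. That contrast assumes the harm has occurred. If instead 5% of patients had recent exposure and each carried a 10% carry-over DLT risk (both assumed), the per-patient risk is 0.10 + 0.05 × 0.10 × 0.90 = 0.1045, and the probability is 0.8955³ + 3(0.1045)(0.8955⁵) ≈ 0.899. Neither figure is the RP2D criterion of at most 1 DLT in 6, which at 10% is 0.9⁶ + 6(0.1)(0.9⁵) = 0.886.
- **Concomitant drugs.** A reader might infer that section 6.4 licenses estrogen or tamoxifen on study, and cite the 38% average fall in letrozole levels with tamoxifen in Appendix C. Section 6.4 speaks in general terms and only of treatment judged necessary for care. The 38% concerns co-administration and does not measure a fault in the washout date. What stands is that 6.4 is silent on the agents listed in item 4.

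**Conclusion.** The concern holds for Phase I. Exclusion 4 applies there, but its reference date may be missing or arbitrarily old. Read literally, it cannot be evaluated for some patients and leaves the period just before cycle 1 day 1 open for others. This is a fault in a stated eligibility rule, and no other section repairs it.

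In Phase II the issue is small. If the reference is T0, at most 14 pre-treatment days are uncovered, and the text needs only to say which biopsy is meant. Section 1.3 says the pre-operative setting "eliminates artifact and variability due to prior therapies as all patients will be previously untreated". Item 4, read with T0 as its reference, is compatible with that aim for the agents it lists, although neither it nor 6.4 says what applies after T0.

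The consequence is possible contamination of the 28-day DLT period by new or worsening carry-over toxicity. Its frequency is unknown, and the probabilities under the objection rest on assumed inputs. They show only that the effect runs from negligible to large depending on those inputs. No alpha, power or sample size changes.

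**What to change.** Amend section 4.2, item 4, keeping the protocol's own intervals and listed agents:

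- **Phase I:** count the 4 weeks (for investigational agents, or 5 half-lives if longer) back from first study treatment, cycle 1 day 1.
- **Phase II:** state that the baseline diagnostic biopsy is the fresh T0 biopsy taken within 2 weeks before therapy.
- **Both phases:** reconcile item 4 with footnote C of section 5.2 and with sections 5.2.1, 5.3.1 and 6.4, so that the protocol says whether the agents already listed are allowed between the reference date and the end of the assessment period (the first cycle in Phase I, T2 in Phase II). That decision belongs to the investigators. No new drug classes or concomitant-treatment rules are proposed here.

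The cost is a wording amendment with no new test or visit. A few Phase I patients may have to wait out the washout. Dropping the biopsy anchor in Phase I costs no listed endpoint, because section 2.1 names safety, response and clinical benefit there, and no tissue measure.
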